16.5.2 Other Safety Measures

The timing and incidence of adverse findings will be compiled following planned surveillance of all study participants by a designated safety monitor.

Vital signs and ECGs will also be evaluated within and between study treatment groups. The overall ECG interpretation will be reported as normal or abnormal; if abnormal, then the percent clinically significant will be reported.

While symptom improvement will be evaluated by assessing changes in the secondary outcome measures (CHRT, MADRS, and CGI-SS), safety measures in the C-SSRS, PRISE, BPRS, and BARS (including the global severity rating) will be evaluated within and between study treatment groups. The timeframe is for both lifetime and the past six months for the baseline Screening scale and since the last visit for the Since Last Visit scale.

16.6 Sample Size Calculations

16.6.1 Background

For DCS treatment group in major depressive disorder Heresco-Levy identified a 0.91 effect size for Hamilton-D Total and a 0.95 effect size for BDI-II (Heresco-Levy, 2013) and an effect size of >1 was seen in the phase 2 STABIL-B study with a similar effect size observed by Chen and Heresco-Levy.

A more modest 0.66 effect size is targeted in the sample size calculations assuming a 1:1 allocation for a two-sided hypothesis test with 5 percent Type I error.

16.6.2 Power and Significance

These sample size calculations are based on the alternative hypothesis corresponding to a 0.66 effect size which corresponds to a mean 8.85-unit MADRS-10 advantage change from baseline for NRX-101 vs control. A total of 74 subjects are to be randomized 1:1 to support the final analysis. As summarized below in Table 6, there is 80% power to detect a 0.66 effect size; a

0.462 effect size would reach two-sided p=0.05. A 0.462 (moderate) effect size reflects a 50 percent drop (based on lurasidone published data) in mean change from baseline for lurasidone with an assumed standard deviation of 13.4; this approximately corresponds to a -16 mean CFB for NRX-101 and a -10 mean CFB for lurasidone.

Table 6 MADRS-10 Change From Baseline Outcomes: T-tests

	Power	Significance
Test significance level, α	0.05	0.05
1 or 2 sided test	2	2
Effect size, $d = m_1 - m_2 / s$	0.66	0.462
Power (%)	80	NA
N per group	37	37

The secondary efficacy hypotheses will also be evaluated using a hierarchical testing strategy where testing continues as long as two-sided p<0.05 is reached. The first such hypothesis to be tested will be for primary endpoint MADRS change from baseline to endpoint, then change from baseline in CGI-SS, followed by time to treatment failure in the NRX-101 and lurasidone groups.

16.6.3 Interim Analyses

Two interim analyses are planned. The first interim analysis (IA) assessing safety will be conducted six weeks after the first 30-35 participants have been followed for 6 weeks and the second IA assessing futility (primary efficacy endpoint) will be performed after the first 45-50 participants have been followed for 6 weeks.

Each interim analysis has a different objective with neither interim analysis spending any Type 1 error. The study will be stopped at the first interim analysis if Serious Adverse Events are deemed statistically significantly more common in the NRX-101 group compared to the lurasidone group in a manner deemed by the DMC to pose a potential danger to human subjects. The study will be stopped at the second IA for futility if the conditional power (CP) is less than 10%. In the event that the study is not stopped for either safety or futility, then enrollment will continue until a total of 74 subjects are randomized. This preserves two-sided p=0.05 for the final analysis.

The unblinded Sponsor biostatistician will perform the interim analyses for the Data Safety Monitoring Board (DSMB). The blinded Sponsor biostatistician will then adjudicate cases with respect to intercurrent events which impact analysis inclusion.

16.7 Adjudication of Primary Endpoint

All rating sessions for MADRS-10 and C-SSRS will be recorded as audio files and reviewed by central master-raters with > 25 years of experience. Any MADRS-10 total score the differs by more than three points from the master-rater score will be deemed non-congruent. All non-congruent subject-visits from any site with > 10% non-congruent scores will be sent to an independent adjudicator, previously determined to have > 90% concordance with study master

raters on standardized training data. In the event of adjudication as above, the independent outside rater score shall be considered as the subject-visit primary study endpoint.

16.8 Statistical Analysis Approach

16.8.1 Software

All calculations will be performed using SAS statistical software, version 9.3 or later, and StatXact, version 10 or later.

16.8.2 Display Formats

All efficacy and safety data will be displayed in tables and listings separately for each treatment group.

16.8.3 Conventions

Study visit dates will be analyzed using the nominal visit instead of the actual visit date.

Means, mean changes, standard deviations, and ranges will be presented separately for each treatment group. These endpoints will be evaluated using a paired t-test and between study treatment groups using an unpaired t-test at each time; these p-values will be presented as descriptive statistics.

For continuous variables, the mean, standard deviation, minimum, median and maximum will be presented, together with the total number of observations and the number of missing and non-missing values.

For ordinal and categorical variables, absolute and relative frequencies will be reported. Relative frequencies will be based on all observations and reported as percentages. Unless otherwise specified, percentages will be based on the number of participants with data and will not be calculated for missing categories.

Adverse events, medical histories, and concomitant medications will be reported on a patient and an event basis. Percentages will be calculated using the number of participants in the Safety population analysis set as the denominator.

All hypotheses will be tested at 5 percent (final analysis) level of significance using a two-sided test unless otherwise specified.

16.8.4 Estimand Structure

Analyses will be conducted in accordance with ICH E9 (R1) analysis principles as summarized below.

Primary scientific question of	The primary study hypothesis is that treatment with NRX-
interest	101 is superior to lurasidone in improving symptoms of
	depression as measured by the MADRS over 6 weeks of
	treatment. The null hypothesis for the primary endpoint is

Target population	the mean change from baseline of MADRS-10 for NRX-101 is the same as lurasidone while the alternative hypothesis is that the mean change from baseline of MADRS-10 is larger than the mean change from baseline of MADRS-10 for lurasidone. Baseline is defined as MADRS-10 score at study entry. The mITT population will be the primary analysis population. The mITT population is defined through
	appropriate inclusion/exclusion criteria as specified in the protocol and blinded BDRM decisions.
Treatment of interest	NRX-101
Outcome Variable	MADRS-10 (and C-SSRS) will be recorded as audio files and reviewed by central master-raters with any non-congruent subject-visits from any site with >10% non-congruent scores sent to a qualified independent adjudicator to be considered as the subject-visit primary study endpoint.
Summary Measure	The contrast-estimated MADRS-10 Week 6 MMRM will use all post-baseline data with LOCF in the mITT population excluding all outcomes after BDRM-approved exclusions. The model will include treatment and the following four baseline stratification factors in addition to baseline MADRS-10: (1) sex, (2) mood stabilizer use, (3) anti-psychotic use, and (4) evidence of suicide event in their lifetime. The model will include treatment group, study visit, the interaction between study visit and treatment group, baseline MADRS-10, and the four baseline covariates as fixed effects. An unstructured error structure will be assumed.
Intercurrent Events	A BDRM will adjudicate all intercurrent events which may redact outcomes after disqualifying events; these intercurrent events may represent major protocol deviations. Any ITT subject with no post-baseline MADRS-10 observations will use the baseline MADRS-10 observation to replace all post-baseline MADRS-10 observations.

16.8.5 General Methodology

The Mixed-Effect Model Repeated Measure (MMRM) will be the primary analysis for the primary efficacy endpoint (MADRS change from baseline); an unpaired t-test will be a secondary analysis. The proportional hazard model (PHREG) will be the primary analysis for time to event endpoints (time to relapse, time to discontinuation); the unstratified log rank test will be a secondary analysis. The MMRM and PHREG models will all include treatment and the following four baseline stratification factors:

- sex
- mood stabilizer use
- anti-psychotic use
- evidence of suicide event in their lifetime.

All primary analyses will be in the ITT population as primary and repeated in the Per Protocol population if >5 percent are excluded.

All of the instruments used to measure SSIB or depression constitute serial continuous and ordinal outcomes that will be analyzed using MMRM with LOCF to account for missing data and early discontinuations. The models will include treatment group, study visit, the interaction between study visit and treatment group, the baseline level of the variable being analyzed, and the above four pre-defined baseline stratification factors as fixed effects. The primary endpoint change from baseline MADRS-10 will be analyzed using the MMRM model which will include baseline MADRS; treatment group; study visit; study visit*treatment; sex, mood stabilizer use, antipsychotic use, and evidence of suicide event in their lifetime as defined above. An unstructured error structure will be assumed.

SAS PROC MIXED will be used for continuous endpoints and PROC GENMOD will be used for binary endpoints.

In addition, multiple imputation will be performed to address any missing data. The method of Little and Rubin will be used. The presentation of the results for the primary efficacy endpoints using the ITT population will be based on the observed data with multiple imputation for missing endpoint data using SAS PROC MI. Missing data will be imputed using MCMC imputation under the assumption of a missing at random using the ITT population. The SAS® procedure PROC MI will be used for the MCMC imputation of 25 complete data sets.

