9.1.2 Treatment and Follow-up Periods

Participants that continue to meet MADRS and C-SSRS eligibility will be randomized to receive the first dose of blinded treatment on Day 1. This visit will be followed by Treatment Period visits at Days 7, 14, 28, and 42. Following completion of the Treatment Period, participants will be

contacted via telephone for follow-up on Day 70. In order to allow scheduling flexibility, and (considering pandemic related limitations), visit windows will be allowed as noted in Table 1. Participants will be withdrawn from the study if their urine toxicology screenings at two consecutive study treatment visits are positive for cocaine, opiates, non-prescribed amphetamines, or non-prescribed barbiturates.

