## **13. REGULATORY STANDARDS**

The study analyses will be conducted in a GCP environment (ICH E6 and E9 [R1]). All analyses will be pre-specified and finalized prior to database lock. If the methods in this SAP do not agree with the protocol, the methods described in the SAP will govern the analysis.

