#### 19.4 Estimand Structure

Analyses will be conducted in accordance with ICH E9 (R1) analysis principles as summarized below.

Primary scientific question of interest	The primary study hypothesis is that treatment with NRX-101 is superior to lurasidone in improving symptoms of depression as measured by the MADRS over 6 weeks of treatment. The null hypothesis for the primary endpoint is the mean change from baseline of MADRS-10 for NRX-101 is the same as lurasidone while the alternative hypothesis is that the mean change from baseline of MADRS-10 is larger than the mean change from baseline of MADRS-10 for lurasidone. Baseline is defined as MADRS-10 score at Visit 2 (randomization).
Target population	The mITT population will be the primary analysis population. The mITT population is defined through appropriate inclusion/exclusion criteria as specified in the protocol and blinded BDRM decisions.
Treatment of interest	NRX-101
Outcome Variables	MADRS-10 (and C-SSRS) will be recorded as audio files and reviewed by central master-raters with any non-congruent subject-visits from any site with >10% non-congruent scores sent to a qualified independent adjudicator to be considered as the subject-visit primary study endpoint.
Summary Measure	The contrast-estimated MADRS-10 Week 6 MMRM will use all post-randomization data with LOCF in the mITT population excluding all outcomes after BDRM-approved exclusions. The model will include treatment and the following four baseline covariates in addition to baseline MADRS-10: (1) sex, (2) mood stabilizer use, (3) anti-psychotic use, and (4) evidence of suicide event in their lifetime. The model will include treatment group, study visit, the interaction between study visit and treatment group, baseline MADRS-10, and the four baseline covariates as fixed effects. An unstructured error structure will be assumed.
Intercurrent Events	A BDRM will adjudicate all intercurrent events which may redact outcomes after disqualifying events; these intercurrent events may represent major protocol deviations.

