## 20. STATISTICAL METHODOLOGY

### 20.1 General Methodology

The Mixed-Effect Model Repeated Measure (MMRM) will be the primary analysis for the primary efficacy endpoint (MADRS change from baseline); an unpaired t-test will be a secondary analysis. The proportional hazard model (PHREG) will be the primary analysis for time to event endpoints (time to remission, time to discontinuation); the unstratified log rank test will be a secondary analysis. The MMRM and PHREG models will all include treatment and the following four baseline covariates:

- sex
- mood stabilizer use
- anti-psychotic use
- evidence of suicide event in their lifetime.

All primary analyses will be in the mITT population as primary and repeated in the Per Protocol population if >5 percent are excluded.

All of the instruments used to measure SSIB or depression constitute serial continuous and ordinal outcomes that will be analyzed using MMRM with LOCF to account for missing data and early discontinuations. The models will include treatment group, study visit, the interaction between study visit and treatment group, the baseline level of the variable being analyzed, and the above four pre-defined baseline stratification factors as fixed effects. The primary endpoint change from baseline MADRS-10 will be analyzed using the MMRM model which will include baseline MADRS; treatment group; study visit; study visit\*treatment; sex, mood stabilizer use, anti-psychotic use, and evidence of suicide event in their lifetime as defined above. An unstructured error structure will be assumed.

SAS PROC MIXED will be used for continuous endpoints.

In addition, supportive analyses will be performed using multiple imputation which will be performed to address any missing data. The method of Little and Rubin will be used. The presentation of the results for the primary efficacy endpoints using the ITT population will be based on the observed data with multiple imputation for missing endpoint data using SAS PROC MI. Missing data will be imputed using MCMC imputation under the assumption of a missing at random using the mITT population. The SAS® procedure PROC MI will be used for the MCMC imputation of 25 complete data sets.

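### The primary MMRM has no baseline-by-visit term, so one baseline MADRS slope adjusts all four visits and part of a chance baseline imbalance can stay in the Week 6 contrast

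*Protocol*

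**What the plan says.** The model is described in four places, and they agree.

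- Protocol 16.8.5 gives an "MMRM model which will include baseline MADRS; treatment group; study visit; study visit*treatment; sex, mood stabilizer use, antipsychotic use" and lifetime suicide event.
- Protocol 16.8.4 (Summary Measure) lists treatment, visit, "the interaction between study visit and treatment group, baseline MADRS-10, and the four baseline covariates as fixed effects".
- SAP 19.4 lists treatment group, "study visit, the interaction between study visit and treatment group, baseline MADRS-10, and the four baseline covariates as fixed effects".
- SAP 20.1 repeats the list: "The primary endpoint change from baseline MADRS-10 will be analyzed using the MMRM model which will include baseline MADRS; treatment group; study visit", then visit by treatment and the same four covariates.

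Baseline MADRS appears once in each list, and visit by treatment is the only interaction. The SAP takes precedence in a conflict (SAP 13: "If the methods in this SAP do not agree with the protocol, the methods described in the SAP will govern the analysis"), but here there is none to resolve.

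The primary contrast is at one visit: "The contrast-estimated MADRS-10 Week 6 MMRM will use all post-randomization data with LOCF in the mITT population" (SAP 19.4). On the covariance, SAP 20.1 says "An unstructured error structure will be assumed". Protocol 9.1.2 gives the post-baseline visits after Day 1: "This visit will be followed by Treatment Period visits at Days 7, 14, 28, and 42". The models for the other scales (Protocol 16.8.7, SAP 20.3) also enter the baseline of the scale once, without a visit interaction.

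**The concern.** The model lets the treatment effect and the covariance differ by visit, but holds the relation between baseline and outcome equal at all four. That relation often weakens with time: an early score tends to follow baseline more closely than a score six weeks later. The fitted slope is then an average over visits, while the primary contrast needs the Week 6 slope. The difference between the two, multiplied by whatever baseline difference randomization happens to produce, stays in the Week 6 estimate.

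Nothing else in the plan supplies a Week 6 slope. Randomization is stratified on a suicidal event in the prior 12 months, not on MADRS (Protocol 16.1, SAP 14). The secondary analysis is an unpaired t-test, which has no baseline covariate. The multiple-imputation analysis is described by how missing values are filled, with no different baseline term.

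**Working it through.** **1. The plan's own figures.** With 37 per arm, 8.85 points and SD 13.4, d = 8.85/13.4 = 0.66. Noncentral t with 72 df gives 80.0% power. The effect size that just reaches p = 0.05 is t(0.975, 72) × √(2/37) = 0.463, or 6.2 points (the plan states 0.462). The stated design reproduces. The standard error of the Week 6 difference is 13.4 × √(2/37) = 3.12 points.

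**2. Algebra.** Leave the four other covariates aside. Let S be the residual covariance over the four visits and b the vector of visit-specific baseline slopes. With every visit filled, as LOCF does:

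- common slope = w′b, with w = S⁻¹1 / (1′S⁻¹1);
- Week 6 estimate = raw Week 6 difference − common slope × baseline difference;
- residual error = (Week 6 slope − common slope) × baseline difference.

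Slopes for change from baseline equal raw-score slopes minus 1, so the gap is the same on either scale.

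**3. Weights and gap.** The documents give only the 6-week SD of 13.4, so the inputs here are assumed. Raw-score slopes are 0.9/0.8/0.65/0.5 at Days 7/14/28/42. The correlation is either 0.7 per 14 days (AR) or 0.5 exchangeable.

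| Residual SDs | Correlation | Weights, Days 7/14/28/42 | Week 6 slope − common slope |
|---|---|---|---|
| 8/10/12/13.4 | AR | 1.04/−0.20/0.02/0.14 | −0.36 |
| 8/10/12/13.4 | exchangeable | 0.69/0.27/0.06/−0.02 | −0.36 |
| 13.4 at all visits | AR | 0.38/0.09/0.12/0.41 | −0.20 |
| 13.4 at all visits | exchangeable | 0.25 each | −0.21 |

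First row in full: 1.04×0.9 − 0.20×0.8 + 0.02×0.65 + 0.14×0.5 = 0.86, and 0.5 − 0.86 = −0.36. Across the steeper decays tried, the gap reached 0.87 in size. With equal slopes at all visits it is 0. A negative gap means that an arm starting higher is over-credited at Week 6.

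**4. Size of the leak.** No baseline SD is stated; assume 3 to 6, given entry at MADRS 30 or more. The standard error of the baseline difference is SD × √(2/37) = 0.70 to 1.39 points. For gaps of 0.1 to 0.5, an imbalance of 2 standard errors moves the estimate by 2×0.1×0.70 = 0.14 up to 2×0.5×1.39 = 1.39 points. That is 4.5% to 45% of 3.12.

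**5. Simulation.** There were 6,000 complete-data trials per case, with AR 0.7. Pairs show the common slope, then visit-specific slopes.

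| Assumed case | Type I error, % | Power at 8.85, % | Movement per point of imbalance (null runs) | Mean absolute change in estimate |
|---|---|---|---|---|
| Moderate: SDs 8/10/12/13.4; slopes 0.9/0.8/0.65/0.5; baseline SD 4 | 4.95, 5.0 | 80.2, 80.4 | −0.33, +0.02 | 0.30 |
| Harsh: SDs 6/9/12/13.4; slopes 0.9/0.7/0.4/0.2; baseline SD 5 | 4.7, 5.0 | 77.3, 79.5 | −0.75, −0.02 | 0.67 |
| Equal SDs of 13.4; slopes 0.8/0.7/0.6/0.5; baseline SD 4 | 5.2, 4.95 | 80.2, 80.0 | −0.07, +0.07 | 0.16 |

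The simulation standard error of a power figure is about √(0.8×0.2/6000) = 0.5 points. In the third case the two movements differ by 0.14, which is the algebraic gap. The 95th percentile of the change is about 1.0, 1.9 and 0.5 points. Mean estimates under the two models agree within 0.01 point in every case.

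**6. How much of the change is imbalance.** The imbalance term alone has mean absolute value gap × SE × √(2/π). That gives 0.358×0.93×0.80 = 0.27 (moderate), 0.735×1.16×0.80 = 0.68 (harsh) and 0.144×0.93×0.80 = 0.11 (equal SDs). It accounts for nearly all of the change in the first two cases and most of it in the third. The rest is noise from estimating more slopes.

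**7. Dropout.** A further simulation of a moderate case gave a movement of about 0.3 per point of imbalance with complete data and about 0.25 with 25% dropout filled by LOCF. LOCF copies early scores into Day 42 and so pulls the Week 6 slope towards the early ones.

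**The case against.** The strongest case against is that this is a valid pre-specified model for which another form is merely preferred. With 74 participants, an unstructured covariance and four further covariates, a single baseline term is a defensible economy. If slopes are constant, the extra terms add only noise. In the equal-variance case above, the planned model had about 0.2 points more power, which is within simulation error. This part stands, and it sets the level of the point.

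Three stronger readings are tempting, and the documents support none of them.

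- A reader might infer that the early visits necessarily drive the common slope. That needs residual variance that rises over visits. It is plausible for a change score, but no early-visit SD is given. With equal SDs, Days 7 and 14 together carry 0.47 to 0.50 of the weight. A gap can remain without early dominance, because Week 6 then has a weight of only 0.25 to 0.41.
- A reader might infer that the primary estimate is biased or the test invalid. Chance imbalance averages to zero, and simulated type I error was 4.7% to 5.2% under the planned model.
- A reader might carry the sizes over to CGI-SS and the other scales. Those models share the form, but no magnitude has been computed for them.

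Two further limits stand. The lower end of the imbalance effect is zero, since it vanishes with constant slopes. The complete-data figures are somewhat too large if dropout is material.

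**Conclusion.** The point holds as a cheap improvement. One baseline slope adjusts four visits while the primary contrast uses one of them, and no other analysis in the plan supplies a Week 6 slope. If the true slope varies over visits, part of any chance baseline imbalance remains in the Week 6 estimate. The remainder is largest where residual variance rises with time, and it favours the arm that starts higher when the slope weakens.

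In the assumed scenarios the estimate changes by about 0.2 to 0.7 points on average, and power gains about 0 to 2 percentage points. Set against the 3.1-point standard error, the 6.2-point significance threshold and the 8.85-point target, this is small, though it could matter for a result close to the threshold. The error is conditional on the imbalance that occurs. It is not systematic bias and does not affect the sample size. Every size here rests on assumed baseline SDs, early-visit SDs, slopes and correlations. If slopes are constant, the two models differ only by slope-estimation noise.

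**What to change.** Before unblinding, add baseline MADRS-10 by visit to the fixed effects of the primary model in SAP 19.4 and 20.1, and bring Protocol 16.8.4 and 16.8.5 into line. In SAP 20.3, add the corresponding baseline-by-visit term for each of the other scales, and match Protocol 16.8.7. If the sponsor prefers to keep the primary model, a pre-specified Day 42 ANCOVA on baseline MADRS as a sensitivity analysis would show a Week 6-specific adjustment.

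The cost is SAP wording and three fixed-effect parameters (four visits minus one), with no new data and no change to 37 per arm. The downside is up to about 2% more variance if the slopes are in fact constant. The timing matters, because the same term added after unblinding would look data-driven.
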